Methods: Consented participants receiving TAU for PTSD at LRTC will be randomized to receive 20 consecutive days of adjunct iTMS according to one of these two treatment arms: **Arm 1** TAU plus iTMS to the right DLPFC or **Arm 2** TAU plus sham iTMS to the right DLPFC. At UTHSCSA's Research Imaging Institute (RII), where all brain imaging and motor threshold assessments will be conducted, iTMS treatment plans will be generated based on (pre-treatment) anatomical and functional magnetic resonance imaging (fMRI) to guide the optimal robotic positioning of the TMS coil to accurately target each subject DLPFC. Participants will be assessed at baseline, during treatment, immediately following treatment and at 1-month post-treatment. A comparison of baseline brain connectivity measurements with subjects' fMRI conducted immediately following treatment will be conducted to identify network connectivity changes potentially associated to treatment response.

Clinical Relevance: This will be the first study to determine the clinical effects of adjunct iTMS delivered to the right DLPFC in the treatment of PTSD, to provide clues about the ideal neural networks to target for more robust clinical outcomes, and to identify potential biomarkers of treatment response including changes in brain networks connectivity.

Item 3 Background	
--------------------------	--

Describe past experimental and/or clinical findings leading to the formulation of your study.

For research involving unapproved drugs, describe animal and human studies.

For research that involves approved drugs or devices, describe the FDA approved uses of this drug/device in relation to your protocol.

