

Item 4 Purpose and rationale Insert purpose, objectives and research questions/hypotheses here. If you cut and paste from another document, make sure the excerpted material answers the question
	
We propose a randomized, double-blind, sham-controlled, 20 consecutive day trial of adjunct TMS to the right DLPFC in active duty service members and veterans with PTSD receiving an integrated and evidence-based treatment (i.e. TAU) for PTSD incorporating both adequate pharmacological approaches and Cognitive behavioral therapy (CBT) at Laurel Ridge Treatment Center (LRTC). In addition to TAU, consented patients will be randomized to receive irTMS in one of two treatment arms: Arm 1 delivers active irTMS to the right DLPFC. Arm 2 delivers sham TMS (inactive coil) to the right DLPFC. To ensure equivalent placebo effects across arms, sham TMS delivers the exact sound produced during active irTMS, therefore patients are unable to discriminate between sham and active TMS. Moreover, clinicians providing TAU at LRTC and researchers conducting clinical outcomes assessments will be blinded to each participants' treatment arm. Resting-state fMRIs (rs-fMRIs) will be used both for treatment planning (baseline imaging), which guides the individualized positioning of the TMS coil, and to characterize TMS-induced network connectivity (imaging treatment week 3). Self-report scales will be done weekly at LRTC. A 1-month post-treatment clinical follow-up will be conducted in person or over the phone to evaluate maintenance of clinical outcomes. Considering that depressive symptomatology, often meeting diagnostic criteria Major Depressive Disorder (MDD), is commonly observed in patients with PTSD, patients with comorbid PTSD and MDD won't be excluded from the study and we will also assess depressive symptoms throughout treatment at the same time intervals—i.e., baseline, weekly, and 1 month post-treatment.
 
Aim 1. Test whether compared with TAU plus sham irTMS, TAU plus adjunct active irTMS is associated with greater clinical improvement that differs in specificity to PTSD or depressive symptomatology according to the targeting of right DLPFC .
 
 Hypothesis 1. TAU plus adjunct active irTMS to the right DLPFC will be superior to TAU plus sham irTMS in relieving PTSD symptoms. 
Aim 2. Test for irTMS-induced changes in network functionality (plasticity) using rs-fMRI.
 
 Hypothesis 2a. Intrinsic connectivity will be attenuated by active irTMS in networks connected to the respective treatment sites, as tested by correlation with the number of sessions received at the time of scanning and by pre-treatment-to-post-treatment contrast. Hypothesis 2b. Treatment-induced decreases in connectivity will correlate with symptom improvement within and across treatment arms.

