Phase I: Baseline MRI. Once the participant has completed the psychological assessments required to determine inclusion/exclusion criteria, eligible participants will be taken from the LRTC to the Research Imaging Institute (RII) at UTHSCSA. When the participant arrives, the participant will undergo an anatomical and functional magnetic resonance imaging (MRI) session. Earplugs will be provided at every MRI session. MRIs use strong magnets and radio waves to non-invasively acquire images of organs and tissues. Unlike X-rays, MRIs do not expose subjects to radiation, therefore it is considered safe to obtain many MRIs in a single scanning session or over multiple days; the initial MRI scans may take up to 2 hours. In the event that the participant cannot tolerate the MRI procedure, they will be withdrawn from the study. Participants will be imaged at the RII using a research-dedicated 3T Siemens TIM/Trio MRI scanner (Siemens, Erlangen, Germany) with an eight-channel phased array coil. Structural imaging will be obtained only once, upon enrollment. Structural images will be used for iTMS treatment planning (described below) and for spatial normalization to a standard anatomical template. MRI images will be obtained two times (i.e. pre-treatment and post-treatment) and used to detect symptom-specific network abnormalities and treatment-induced plasticity. We will also perform motor threshold assessments for each patient (at pre-treatment and post-treatment, immediately after each MRI) to determine the correct intensity and train durations needed to safely deliver iTMS in each patient's 3-Week Treatment Phase. The post-treatment motor threshold assessment are important to the future establishment of safety guidelines for iTMS treatment of PTSD.

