The right DLPFC treatment target locations will be based on connectivity strength with ACC and Precuneus using region-seeded resting-state BOLD fMRI. Coil orientation will be corrected for the underlying gyral anatomy, using a T1-MRI derived cortical surface model to align the E-field according to the cortical column cosine model. Stimulation intensity will be corrected for the distance of the stimulation site from the scalp/coil surfaces. Intensity ranges will be individually adjusted for each patient—to deliver depth-corrected E-fields between 80 volts/meter and 95 volts/meter.

Sham TMS: An image-guided treatment plan will be computed for sham TMS subjects in the same manner as for active irTMS to ensure therapist blinding.

irTMS Treatment Sessions. All participants will continue with their TAU at LRTC (or its treatment clinics) including regular medication management encounters with their attending psychiatrist and therapy sessions as of their treatment. An effort will be made to limit the disruptions in patients' TAU by working research assessments and irTMS around their expected TAU programming. irTMS treatment visits will take place at the LRTC starting as soon as possible after the treatment plan is completed, expected to be 1-2 working days following baseline scanning.

irTMS Position/Holding. For each subject, the coil pose will be pre-computed from structural and functional MRI and stored as an individualized treatment plan. Each subject's treatment plan will be registered to his/her head by creating a scalp model with a high-resolution digitizer, an integrated component of the irTMS system. In each arm,

the TMS coil will be positioned and held by the robot (under the treatment technician's supervision).

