TMS treatment guidelines recommend that the train duration of TMS pulse protocols remain within the limits of published safety guidelines (reached by a consensus of TMS practitioners). For example, if a patient requires a TMS intensity equivalent to 130% of their motor threshold, then we must limit our TMS train durations to 0.55 seconds (i.e. 11 pulses/train). Therefore, we will adjust the train duration of each patient's treatment protocol so that it falls within the limits of these recommendations. We will also adjust the intertrain interval to ensure that we deliver all of our treatment pulses within the hour-long treatment session. For example, if a patient needs a TMS intensity equivalent to 130% of their resting motor threshold, we will deliver 160 pulse trains of irTMS (e.g. train duration = 0.5 seconds; intertrain interval = 7.5 seconds; 10 pulses per train), which would require 21.33 minutes of treatment time to deliver the desired number of TMS pulses in each session (i.e. 1,600 pulses). The primary TMS treatment parameters (TMS frequency (i.e. 20Hz), number of pulses per session (i.e. 1,600), and number of sessions (i.e. 20) will remain the same across patients. We may only adjust the patient's intensity and the protocol's train duration and intertrain intervals so that they fall within the safety limits of repetitive TMS treatments.

Active treatment will use a liquid cooled figure-8 MagPro coil (MagVenture, Denmark). Sham treatment will use a coil that simulates the sound and scalp stimulation of TMS but does not deliver an E field (MagVenture, Denmark).

Participants will receive treatment 7 days per week for as long as they are hospitalized at LRTC for up to 20 sessions. On each treatment day, a total of 1,600 pulses will be administered within the one hour TMS session. With the set up for treatment, the total time required for each treatment visit should be less than one hour per day. This protocol will administer a total of 24,000 pulses over the three-week period. If study participants decide, at any time, that they cannot tolerate the irTMS treatments, they will be withdrawn from the study (see Discontinuation and Withdrawal of Patients Section below) and will be assisted in finding appropriate after-study care.

Phase II: Post-Treatment Follow-Up

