Intrinsic Connectivity by BOLD fMRI. Data will be analyzed using FSL's FEAT program. Head movements are corrected by affine registration using a 2-pass procedure. BOLD data will be normalized to MNI space single-patient template using the "unified segmentation" approach, followed by a 5-mm full width at half maximum Gaussian smoothing. Spurious correlations with nuisance variables are removed using a recently validated framework. Data are band-pass filtered preserving frequencies between 0.01 and 0.08 Hz. The time course of each seed region's BOLD signal will be extracted as the first eigenvariate of activity in all gray-matter voxels located within the respective cluster. To quantify resting-state functional connectivity linear (Pearson) correlation coefficients between the time series of the seeds (targeted DLPFC nodes of each patient's DLPFC-limbic and DLPFC-motor networks) and any other gray matter voxel will be computed. Voxel-wise correlation coefficients will be transformed into Fisher's Z-scores (with non-sphericity correction). These images will be used for iTMS treatment planning. The resting-state fMRI scan will also be used to assess, network-specific functional connectivity differences between each patient's pre-treatment and post-treatment scans.

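### Hypothesis 2a attributes reduced connectivity to active irTMS, but its pre-to-post contrast does not state a comparison with sham, so it cannot separate irTMS from treatment as usual or time

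*Combined protocol and SAP*

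**What the plan says.** Item 4, Aim 2, Hypothesis 2a predicts that active irTMS will weaken intrinsic connectivity in the networks linked to the stimulated site, "as tested by correlation with the number of sessions received at the time of scanning and by pre-treatment-to-post-treatment contrast". The sham arm is not mentioned.

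The neighbouring hypotheses differ:
- Hypothesis 1 names its comparator: "TAU plus adjunct active irTMS to the right DLPFC will be superior to TAU plus sham irTMS in relieving" PTSD symptoms.
- Hypothesis 2b mentions arms, but for another question: decreases in connectivity "will correlate with symptom improvement within and across treatment arms".

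The other imaging text does not add a comparator:
- Item 2, Methods, compares baseline connectivity with fMRI "conducted immediately following treatment will be conducted to identify network connectivity changes potentially associated to treatment response".
- Item 6, Data Analysis, Intrinsic Connectivity by BOLD fMRI, says the resting-state scan will be used to assess "network-specific functional connectivity differences between each patient's pre-treatment and post-treatment scans".
- The mixed effects models in the Clinical Outcomes Data Analysis plan are given for PCL-5 and CAPS-5.

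On the setting, Item 6 keeps every participant on TAU during the treatment phase (irTMS Treatment Sessions) and schedules two functional scans per patient (Phase I: Baseline MRI). The planned "number of sessions (i.e. 20) will remain the same across patients" (irTMS Treatment Protocol). The Table of Study Procedures makes no arm distinction for either scan.

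**The concern.** Hypothesis 2a is causal, but a change within patients is not specific to the cause it names. Between the scans every patient receives medication management and psychotherapy, and about three weeks pass. If either lowers connectivity in the target networks, the pre-to-post contrast will show a decrease whether or not irTMS does anything. An analyst following Item 4 and the imaging section literally could report that as plasticity induced by irTMS. The randomised sham arm, scanned on the same schedule, is what separates the two explanations, and the plan does not say that it will be used for this hypothesis.

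The session-count correlation might be expected to supply the missing control. Whether it does depends on two things the plan leaves open: whether both arms enter, and whether sham sessions are counted.

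**Working it through.** **The plan's own figures.** The documents give no effect size, error rate or power for Hypothesis 2a, so there is nothing to reproduce. From the documents come 50 completers per arm (Item 6, Step-by-Step Methods) and the scan days (Table of Study Procedures: baseline MRI day 2-3, post-treatment day 21-24). The scan gap is therefore 21 − 3 = 18 to 24 − 2 = 22 days.

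**Assumptions.** One connectivity measure, tested once, two-sided 5%; effects in SD of pre-to-post change; the same TAU or time drift in both arms, in the predicted direction (lower connectivity). Signs are dropped below.

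**Pre-to-post contrast, true irTMS effect zero.** For a paired t-test the noncentrality is drift × √n.

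| Drift (SD) | Active arm, n = 50: noncentrality | Significant | Both arms pooled, n = 100: noncentrality | Significant |
|---|---|---|---|---|
| 0.1 | 0.71 | 11% | 1.0 | 17% |
| 0.2 | 1.41 | 28% | 2.0 | 51% |
| 0.3 | 2.12 | 55% | 3.0 | 84% |
| 0.5 | 3.54 | 93% | 5.0 | 99.9% |

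**Active versus sham, same drift.** The expected difference in change is drift − drift = 0, so the rate stays at 5%.

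**Session-count correlation.** The session spread is unknown, so three patterns for 50 patients are assumed:
- A: 45 patients at 20 sessions, five at 16 to 19 (SD 0.76).
- B: 40 patients at 20, ten at 12 to 19 (SD 1.96).
- C: an even spread from 10 to 20 (SD 2.97).

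*Reading 1: active arm only, second scan only.* Drift is not the main problem here; lack of information is. A true 1 SD effect over 20 sessions is 1/20 = 0.05 SD per session, so r is about 0.05 × SD of counts: 0.04 (A), 0.10 (B), 0.15 (C). Power with 50 patients is about 6%, 10% and 18%.

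*Reading 2: both scans, baseline counted as zero sessions, patient effect in the model.* This reduces to regressing change on sessions through the origin, which is close to the pre-to-post contrast. Simulated false-positive rates, with no irTMS effect and drift proportional to sessions:

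| Drift (SD) | A | B | C |
|---|---|---|---|
| 0.2 | 28% | 27% | 19% |
| 0.3 | 54% | 52% | 35% |
| 0.5 | 93% | 92% | 76% |

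As a plain correlation ignoring the pairing (test-retest correlation 0.5), the rates at 0.5 SD drift are 76%, 73% and 48%.

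*Reading 3: both arms, second scan, sham patients coded as zero active sessions.* This is close to the randomised contrast. False positives are about 5%. Power at a true 0.5 SD is about 69% (A), 68% (B) and 50% (C).

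**Power of the proposed test.** On change scores with 50 per arm, noncentrality at 0.5 SD is 0.5 × √(50/2) = 2.5, giving 70% power. Baseline adjustment multiplies the SD by √((1 + ρ)/2), where ρ is the test-retest correlation:
- ρ = 0.3: 0.5/0.806 = 0.62 SD, 87% power.
- ρ = 0.5: 0.5/0.866 = 0.58 SD, 82% power.
- ρ = 0.7: 0.5/0.922 = 0.54 SD, 77% power.

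The smallest effect with 80% power is 0.57 SD between arms on change scores, against 0.40 SD within one arm.

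**The case against.** The trial is randomised and sham-controlled, both arms follow the same scan schedule, and calling the stimulation active presupposes sham as its counterpart. Item 4 is an aims box in an institutional template, and the imaging section is mostly about preprocessing. The pre-to-post contrast may simply name the quantity to be compared between arms. The plan is equally brief about the primary outcome. All this stands to the extent that nothing in the documents rules out a sham comparison. But Hypothesis 2a does list its tests, and no section states an active-versus-sham test of connectivity change.

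It is also fair to say that the session-count test can be valid: Reading 3 is. A reader might infer that this correlation is uninformative however it is run. The documents do not support that, because they do not settle which reading is meant.

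Two limits on the error rates stand. Drift would falsely support the hypothesis only if it lowered connectivity; drift upward would work against it, and the documents give neither sign nor size. The imaging section describes voxel-wise maps, so a calculation for one measure shows the mechanism and does not predict the planned analysis.

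Item 6 says that early post-treatment scans and non-compliance will be taken into account in the analysis. That deals with shortfall in sessions and leaves the comparator open.

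**Conclusion.** The point holds as a gap in the analysis specification. As written, a within-arm or pooled pre-to-post decrease cannot be credited to irTMS, and the session-count correlation repairs this only under a coding that the plan does not state. Under the assumptions above, drift of 0.1 to 0.5 SD in the predicted direction would make the active-arm contrast significant in 11% to 93% of trials with no irTMS effect, against 5% for active versus sham.

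A reader might infer that the design cannot answer Aim 2, or that the primary result is in doubt. Neither follows. The sham arm and both scans are already planned, and the PCL-5 and CAPS-5 analyses are not touched. This is a cheap improvement to a mechanistic aim.

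**What to change.** In Item 4, Hypothesis 2a, and in the Intrinsic Connectivity analysis section, name the active-versus-sham difference in pre-to-post connectivity change as the test. Use either post-treatment connectivity adjusted for baseline or an arm-by-time term. Keep the within-arm contrast and the session-count correlation as supportive analyses, and state which arms and scans enter the correlation and how sham sessions are coded.

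The cost is wording and a little analysis, with no extra scans or patients. The price in power is the drop from a nominal 93% within-arm to 70% between arms at a true 0.5 SD, mostly recovered by baseline adjustment when test-retest correlation is low. The 93% is not a real advantage, since drift of 0.5 SD alone gives the same figure.

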COVER PAGE FOR PROTOCOL AND STATISTICAL ANALYSIS PLAN

Official Study Title: Image-guided, Robotically Delivered TMS Treatment for Combat-Related PTSD

NCT number: NCT 02853032

IRB Approval Date: 03/04/2020

Unique Protocol ID: HSC20160191H

Protocol Template Form

Item 1 UTHSCSA Tracking Number	HSC20160191H
---------------------------------------	--------------

Item 2 Abstract / Project Summary

Provide a succinct and accurate description of the proposed research. State the purpose/aims. Describe concisely the research design and methods for achieving the stated goals. This section should be understandable to all members of the IRB, scientific and non-scientific.

DO NOT EXCEED THE SPACE PROVIDED.

Purpose/Objectives: Mounting amounts of evidence suggests that non-invasive stimulation of the dorsolateral prefrontal cortex (DLPFC) using image-guided, robotically-delivered transcranial magnetic stimulation (iTMS) maybe a safe and effective treatment modality for Posttraumatic Stress Disorder (PTSD). However the large variability in the magnitude of clinical outcomes reported is likely related to the current lack of knowledge of ideal location of stimulation and the limited precision in the targeting of brain circuits needed to obtain an optimal treatment response. In this protocol we will: 1) generate individualized treatment plans based on an individual's functional Magnetic Resonance Imaging (fMRI) and meta-analytical based connectivity analysis to guide the delivery of adjunct, iTMS to active duty military service members and veterans with PTSD participating in an intensive program providing integrated evidence-based psychotherapy and pharmacological management (Treatment as Usual (TAU)). 2) To use clinician ratings and self-report PTSD symptom scales, as well as other indicators of clinical change, to determine whether compared with TAU, addition of adjunct iTMS improves clinical outcomes. 3) To conduct neuroimaging-based assessments aimed to measure iTMS effects on network connectivity in service members and veterans receiving treatment for PTSD and the potential correlation of connectivity changes with clinical outcomes.

Research Design/Plan: Randomized, double-blind, sham-controlled clinical trial.

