Step-by-Step Methods: We propose to test 100 patients (i.e. 50 per arm) who meet criteria for PTSD as determined by the Clinician Administered PTSD Scale (CAPS-5) and the outlined study inclusion criteria. We anticipate consenting and screening approximately 200 male and female subjects, in order to meet the target enrollment goals. To account for subject dropouts and retain a sample of 100 subjects completing the double-blind treatment phase (50 per treatment group), 132 eligible subjects (66 in each group) meeting the study inclusion criteria will be randomized for the study. See also Table of Study Procedures below.

Recruitment

Patients will be recruited at LRTC from institution's PTSD inpatient program by the study staff supervised by the On-site Investigator's team. Upon admission to the LRTC, patients will be informed about this treatment trial by either their staff psychiatrist or a member of the LRTC's research team. Each patient will be given an information sheet describing the study. If interested in participating, each patient will be shown a video describing the treatment trial and each of the tools/treatments used throughout the study (i.e. MRI and TMS).

Pre-Screening and LRTC Intake

Under an IRB approved HIPAA Waiver of Authorization, Waiver of Informed Consent, and Waiver of Documentation of Informed Consent, study personnel will conduct a brief pre-screening intake interview where the basic study inclusion and exclusion criteria will be reviewed to help the individual determine if he or she meets the study criteria or has obvious exclusions from the study protocol. This information will be maintained as a secure file with the following information: name, phone number, name of study, referral date, referral source, potential eligibility status, reason if not eligible, and verbal permission to contact the caller in the future for other studies. Subjects who agree to study participation will sign a consent document before any further screening will take place. Any individually identifiable information and Protected Health Information (PHI) collected on individuals who do not consent to participation will not become part of the research data. If subjects agree to participate in the research, the identifiable data collected will become part of the subjects' research records and will be stored according to the research confidentiality plan.

Consent Process

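### Hypothesis 2b has no analysis model; read as a simple pooled correlation, its cross-arm test mixes the treatment effect with the patient-level association

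*Combined protocol and SAP*

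**What the plan says.** Item 4, Aim 2, Hypothesis 2b states that treatment-induced decreases in connectivity "will correlate with symptom improvement within and across treatment arms". Two other hypotheses in Item 4 bear on it. Hypothesis 2a expects that "Intrinsic connectivity will be attenuated by active irTMS in networks connected to the respective treatment sites". Hypothesis 1 expects that active treatment "will be superior to TAU plus sham irTMS in relieving" PTSD symptoms.

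Item 2 lists among the objectives the "potential correlation of connectivity changes with clinical outcomes", and its Clinical Relevance paragraph says the study is "to identify potential biomarkers of treatment response including changes in brain networks connectivity".

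The Data Analysis part of Item 6 does not return to Hypothesis 2b. The paragraph on intrinsic connectivity says only that resting-state scans will be used to assess "network-specific functional connectivity differences between each" patient's scans before and after treatment. The Clinical Outcomes Data Analysis plan names mixed effects regression for the primary clinical analysis and does not link it to connectivity. No text says whether the cross-arm correlation is adjusted for arm, whether the within-arm or the cross-arm result is decisive, or which symptom score and time point are meant.

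**The concern.** If active stimulation lowers connectivity and also improves symptoms, active patients sit higher on both axes (connectivity decrease, symptom improvement) and sham patients lower. Pooling the two groups produces a positive correlation even if, inside each arm, patients with larger connectivity changes do no better than the others. That correlation shows that treatment moved both measures. It does not show that connectivity change tracks response from patient to patient, which is what a biomarker claim requires. The setting in which this happens is the one that the trial's own hypotheses predict.

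At stake is the interpretation of the imaging aim: a connectivity biomarker could be reported that mainly reflects arm membership. If a real within-arm association exists, pooling can still misstate its size in either direction.

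**Working it through.** **Plan's own figure.** The documents state no sample size, power or effect size for Hypothesis 2b, so there is no figure to reproduce. The only input they give is the number of patients. Item 6 says "We propose to test 100 patients (i.e. 50 per arm") should complete treatment, with "132 eligible subjects (66 in each group") randomized. That implies a loss of 1 − 100/132 = 24.2%. I use 50 per arm.

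**Assumptions not in the documents.** Two-sided 5% test; normal data with equal SDs in both arms; arm differences d₁ (connectivity decrease) and d₂ (symptom improvement) in within-arm SD units, from 0 to 1; within-arm correlation ρ_w of 0 or 0.3.

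**Step 1: what pooling estimates.** With 1:1 allocation, the arm difference adds d₁d₂/4 to the covariance and d²/4 to each variance:

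ρ_pool = (ρ_w + d₁d₂/4) / √[(1 + d₁²/4)(1 + d₂²/4)]

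With ρ_w = 0 and d₁ = d₂ = d this is (d²/4)/(1 + d²/4):

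- d = 0.2: 0.01/1.01 = 0.010
- d = 0.3: 0.0225/1.0225 = 0.022
- d = 0.5: 0.0625/1.0625 = 0.059
- d = 0.8: 0.16/1.16 = 0.138
- d = 1.0: 0.25/1.25 = 0.200

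**Step 2: how often the test rejects when ρ_w = 0.** Simulated trials, 50 per arm:

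| d₁ / d₂ | Pooled, unadjusted | Arm-adjusted | Within one arm |
|---|---|---|---|
| 0 / 0.5 | 5.0% | 5% | 5% |
| 0.2 / 0.2 | 5% | 5% | 5% |
| 0.3 / 0.3 | 6% | 5% | 5% |
| 0.5 / 0.5 | 9% | 5% | 5% |
| 0.5 / 0.8 | 15% | 5% | 5% |
| 1.0 / 0.5 | 19% | 5% | 5% |
| 0.8 / 0.8 | 28% | 5% | 5% |
| 1.0 / 1.0 | 53% | 5% | 5% |

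The five rows with equal differences were run again with 200,000 trials each; the pooled rates were 5.1%, 5.5%, 9.0%, 28.0% and 52.7%.

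**Step 3: requiring both results.** In the same runs, if support needs the pooled test and the active-arm test both to be significant, false support occurs in 1.6% to 2.6% of trials. If it needs the pooled test and either single-arm test, the range is 3.1% to 5.0%.

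**Step 4: when a real association exists (ρ_w = 0.3).** Pooling gives 0.341 at 0.5/0.5, 0.397 at 0.8/0.8, and 0.224 when the arm differences run in opposite directions (0.5/−0.5). The arm-adjusted test has about 86% power; each single-arm test has about 57%.

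**The case against.** The strongest reply is that Hypothesis 2b is a scientific hypothesis in the purpose section, not an analysis specification. A reader might infer that the plan prescribes unadjusted pooling. It does not: the cross-arm wording could mean an adjusted or stratified analysis, or consistency over the arms. This stands. The fault is an unspecified analysis whose plainest reading is confounded by treatment, not a wrong method laid down in the text.

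Second, the same clause plans within-arm correlations, and these are unaffected. Read literally, the hypothesis needs both results, and step 3 shows that false support would then be about 5% or less. This also stands, but only if both are required. No text says so, and each within-arm test has half the sample and about 57% power at a correlation of 0.3. The pooled result could therefore end up as the reported one, although nothing in the documents plans selective reporting.

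Third, a reader might infer that pooling gives a false association whenever the arms differ. That is too strong. Inflation is negligible at 0.2 to 0.3 SD and absent if only one measure differs. Both arms receive intensive usual treatment, and nothing in the documents supports differences of 0.8 to 1.0 SD on both measures. Nor is a pooled correlation false as a description when treatment moves both measures; mediation would produce one too. What fails is reading it as a patient-level association, because it cannot separate mediation from two unrelated treatment effects.

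Finally, the aim is worded in exploratory terms and primary efficacy is untouched. That limits the weight of the point without removing it.

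**Conclusion.** The point holds in limited form. Hypothesis 2b has no model, no arm term and no decision rule, and an unadjusted cross-arm correlation would mix the treatment effect with the patient-level association in the setting that Hypotheses 1 and 2a predict. The size depends wholly on arm differences that the documents do not give. Under the stated assumptions the false-positive rate runs from practically nominal at 0.2 to 0.3 SD, through 9% at 0.5 SD, to 28% at 0.8 SD and 53% at 1.0 SD. The documents do not support the stronger conclusion that the trial is set to produce a spurious biomarker: that needs unadjusted pooling, sizeable differences on both measures, and disregard of the within-arm results. The consequence is confined to a secondary mechanistic aim. It is still worth correcting, because the arm-adjusted test uses the whole sample, holds 5%, and is much more powerful than either single-arm test.

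**What to change.** Add a short paragraph on Hypothesis 2b to the Data Analysis part of Item 6, before the blind is broken:

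- **Cross-arm analysis:** regress symptom change on connectivity change with arm as a covariate. Baseline symptom score may be added. Name the symptom score and time point.
- **Decisive test:** the common arm-adjusted connectivity slope, for any biomarker claim.
- **Interaction:** test arm by connectivity in a separate model as a secondary check. In the main model it would turn the connectivity coefficient into an arm-specific slope and leave the decisive test undefined.
- **Within-arm correlations:** keep them as planned.
- **Raw pooled correlation:** report it as a description only.

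The cost is a few sentences, one degree of freedom for arm, one more if baseline is added, and one in the separate interaction model. No new data are needed. The rates above were computed for adjustment by arm alone; the optional baseline term was not simulated.
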